8.5.7. HbA1c, Serum Chemistry, and Hematology

Central laboratory results will be summarized using International System (SI) of units. The laboratory results will be summarized by treatment and visit. The parameters within each panel are outlined in Section 8.4.6.1 of the trial protocol, and lab panels for hematology and serum chemistry will be included.

Shift tables (i.e., low, normal, high at baseline versus low, normal, high at follow-up in a 3-by-3 contingency table) will be provided to assess changes in laboratory values from baseline to follow-up result at each scheduled follow-up visit. The counts and percentage of participants with each of the 9 possible "shift" outcomes will be calculated by treatment group. Individual laboratory data from scheduled and unscheduled visits will be listed.

Additionally, the number of subjects with the following lab parameters of special interest will be summarized descriptively by treatment group:

8.5.8. Retinal Fundoscopy

Retinal fundoscopy findings in each eye (presence or absence of proliferative retinopathy, other finding) at screening (Baseline) and the Day 180 visit and any changes from the baseline at the follow-up visits will be summarized descriptively by treatment group.

8.5.9. Electrocardiogram (ECG)

The collected ECG values will be listed.

8.6. Other Clinical Parameters

8.6.1. Total Acetaminophen (Rescue Medication) Dose

The number and percentage of participants taking acetaminophen between baseline and Day 90, Day 90 and Day 180 and baseline and Day 180 will be calculated by the treatment group. The number and percentage of participants taking acetaminophen between baseline and Day 90, Day 90 and Day 180 and baseline and Day 180 will be summarized by the treatment group. The mean, standard deviation, minimum, maximum, median, and 1st and 3rd quartiles of days to the first start date of the acetaminophen will be summarized by the treatment group using observed data; participants not taking acetaminophen will not be included in these descriptive statistics. The total dose of acetaminophen of each participant between baseline and Day 90, Day 90 and Day 180 and baseline and Day 180 will be summarized by the treatment group. These analyses will be based on the ITT and PP Dosing population.

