## **6.8. Prior and Concomitant Medications, Treatments, and Procedures**

Medications and treatments taken within 30 days prior to Day 0 will be recorded on the Medication and History eCRF at the Day 0 Visit. Any medication or vaccine, including over-the-counter or prescription medicines, vitamins, herbal supplements, and topical anesthetics for post-injection pain and procedures that the Participant is receiving at the time of enrollment or receives during the study must be recorded on the Concomitant Medications or Concomitant Procedures eCRF.

For each medication or treatment, the following information will be collected:

- Medication trade or generic name, or procedure
- Indication for which the medication/procedure was given
- Dose/strength, route, and frequency of administration
- Date started and date stopped (or continuation at study exit)
- Reason for use

The Medical Monitor will be contacted if there are any questions regarding concomitant or prior therapy. Acetaminophen is the only rescue medication allowed in this study. Up to 3 grams per day will be allowed. Use of rescue medication will be recorded each day in the eDiary.

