### 9.3.3. Exploratory Efficacy Endpoints

The exploratory efficacy endpoints include the following:

- Patient Global Impression of Change (PGIC) on Day 90 and on Day 180 for Engensis compared to Placebo
- Proportion of Responders (based on  $\geq 50\%$  reduction in the means of ADPS from the BPI-DPN) from the 7 days prior to Day 180 who were Responders on Day 104 (final injection visit) for Engensis compared to Placebo
- Changes in the Bedside Sensory Testing (BST) from Baseline to Day 90 and to Day 180 for Engensis compared to Placebo
- Proportion of Responders ( $\geq 20, 30, 40, 60$  and  $70\%$  reduction in the means of ADPSs from the BPI-DPN) from the 7 days prior to the Day 0 Visit to the 7 days prior to the Day 90 Visit and the 7 days prior to the Day 180 Visit for Engensis compared to Placebo
- Changes in the means of the Average Daily Pain Scores (ADPSs) from the BPI-DPN from the 7 days prior to the Day 0 Visit to the 7 days prior to the Day 90 Visit for Engensis compared to Placebo
- Changes in the severity scores (Worst Pain, Least Pain, Average Pain, and Pain Right Now) from the full BPI-DPN from the 7 days prior to the Day 0 Visit to the 7 days prior to the Day 90 Visit and the 7 days prior to the Day 180 Visit for Engensis compared to Placebo
- Changes in Michigan Neuropathy Screening Instrument (MNSI) assessments from Baseline to Day 90 and to Day 180 for Engensis compared to Placebo
- Changes in Quality of Life in the SF-36 from Baseline to Day 90 and Day 180 for Engensis compared to Placebo
- Changes in Quality of Life in the EQ-5D from Baseline to Day 90 and to Day 180 for Engensis compared to Placebo
- Changes in the means of the daily use of rescue medication from Day 0 to Day 90, from Day 0 to Day 180, and from Day 90 to Day 180 for Engensis compared to Placebo

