4.5. Other Clinical Parameters

Total acetaminophen (rescue medication) used during the study

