7.6.2. Addressing Missing Data for the Secondary and Exploratory Efficacy

Missing individual item scores of the full BPI-DPN will be imputed for the calculation of the average score within a domain using the average score across the non-missing items within the domain at a subject's visit provided that the proportion of missing items scores within that domain is less than 25%; otherwise, the domain score at that visit is missing.

The same method as the full BPI-DPN will be used when addressing the missing data for SF-36 and EQ-5D.

Individual item scores on the MNSI (both physical assessment and history) questionnaire will not be imputed. The total MNSI scores will be imputed using a "worst-case" imputation approach. Missing individual items will be imputed as the category corresponding to the largest number of points in the total score calculation. This equates to a response of "Yes" to questions 1-3, 5-6, 8-9, 11-12, and 14-15 and "No" to questions 7 and 13 on the history assessment. On the physical assessment, it equates to a response of "No" on the "Appearance of Feet" question, a response of "Present" on the "Ulceration" question, and a response of "Absent" on the "Ankle Reflexes", "Vibration perception at great toe", and "Monofilament" questions.

Missing PGIC and BST scores and the use of rescue medication will not be imputed.

Missing values from the cytokine profiles and anti-hepatocyte growth factor (HGF) antibody results will not be imputed as they are a part of the safety assessment.

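### SAP 8.6.1 summarises rescue acetaminophen as an interval total not divided by days observed, and time to first use among users only, while the protocol's exploratory endpoint is mean daily use

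*SAP*

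**What the plan says.** Protocol 9.3.3, like the Synopsis and Section 3, lists as an exploratory efficacy endpoint "Changes in the means of the daily use of rescue medication from Day 0 to Day 90, from Day 0 to Day 180", and also from Day 90 to Day 180. Protocol 6.8 provides the data: "Use of rescue medication will be recorded each day in the eDiary".

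The SAP handles rescue use differently:

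- The Section 2 endpoint table otherwise follows the protocol's exploratory list but ends at EQ-5D, without the rescue endpoint. The visible part of the exploratory list in Section 4 also ends at EQ-5D.
- Section 4.5, Other Clinical Parameters, names "Total acetaminophen (rescue medication) used during the study".
- Section 8.6.1 plans three summaries by arm. The first is "The number and percentage of participants taking acetaminophen between baseline and Day 90", with the same for the other two intervals. The second is days to first use, for which "participants not taking acetaminophen will not be included in these descriptive statistics". The third is "The total dose of acetaminophen of each participant between baseline and Day 90, Day 90 and Day 180 and baseline and Day 180". The populations are ITT and one labelled PP Dosing.
- Section 7.6.2 adds: "Missing PGIC and BST scores and the use of rescue medication will not be imputed".

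**The concern.** A total over a fixed interval measures two things at once: how much a participant takes per day and how many days that participant is observed. The ITT population includes early leavers. If observed doses are simply summed, someone who leaves on Day 30 contributes 30 days of use to a 180-day total and looks like a light user. A daily mean removes that dependence, and it is what the protocol names.

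Days to first use has a separate weakness. Restricting it to users selects on something that happens after randomisation and that treatment may change. Participants who never need rescue, the best result on this measure, drop out of the statistic.

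Acetaminophen is the only rescue permitted for neuropathic pain and may affect the pain score, so readers will want the rescue comparison beside the primary result. What is at stake is how clearly that comparison can be read, not the primary test.

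**Working it through.** The plan states no figure for rescue use, so there is none to reproduce. It also gives no dropout or rescue rate. Every rate below is an assumption chosen to show size and direction.

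**Inputs**

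| Input | Value | Source |
|---|---|---|
| Follow-up | 180 days | Protocol Synopsis |
| Rescue record | daily eDiary | Protocol 6.8 |
| Total dose | per participant, no per-day scaling | SAP 8.6.1 |
| Days to first use | users only | SAP 8.6.1 |
| Dropout d | 0% to 30% per arm, exits uniform over 180 days | assumed |
| Daily use r | 1 g/day, equal in both arms | assumed; cancels in the ratio |
| Share using rescue by Day 180, p | 40% to 80% | assumed |

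**Step 1: total dose.** With uniform exits, leavers are observed for half the period on average:

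expected total = r × 180 × (1 − d/2).

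| Dropout, arm A vs arm B | Total A (g) | Total B (g) | Ratio of totals | True ratio of daily use |
|---|---|---|---|---|
| 10% vs 10% | 171 | 171 | 1.000 | 1.000 |
| 20% vs 10% | 162 | 171 | 0.947 | 1.000 |
| 20% vs 5% | 162 | 175.5 | 0.923 | 1.000 |
| 30% vs 10% | 153 | 171 | 0.895 | 1.000 |
| 30% vs 0% | 153 | 180 | 0.850 | 1.000 |

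Dose per observed day recovers the true ratio in every row. If arm A truly used 10% more per day, then at 30% against 10% dropout the ratio of totals would be 1.10 × 0.85/0.95 = 0.984, so the direction would be lost. That case needs a 20-point gap in dropout.

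Interval length also varies among completers. The Schedule of Activities gives Day 90 and Day 180 windows of ±7 days, so the second interval can run from 173 − 97 = 76 days to 187 − 83 = 104 days. This adds noise to a total, not bias between arms.

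**Step 2: days to first use, constant hazard.** With L = −ln(1 − p)/180:

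- users-only mean = 1/L − 180(1 − p)/p
- restricted mean to Day 180, all participants = p/L

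For p = 0.80: 1/L = 111.8, so the users-only mean is 111.8 − 45.0 = 66.8 days and the restricted mean is 89.5 days.

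For p = 0.50: 1/L = 259.7, so the users-only mean is 259.7 − 180.0 = 79.7 days and the restricted mean is 129.8 days.

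The arms differ by about 13 days on the users-only mean and about 40 days on the restricted mean. The direction is the same, and the users-only gap is about a third of the size.

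**Step 3: days to first use, fewer users with unchanged timing.** Let the share of users fall from 80% to 40%, with a mean of 40 days among users in both arms. The users-only means are 40 and 40 days. The restricted means are 0.8 × 40 + 0.2 × 180 = 68 days and 0.4 × 40 + 0.6 × 180 = 124 days. The users-only statistic shows no difference, but the percentage-of-users table would show 80% against 40%.

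**The case against.** Four objections have force.

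**The SAP may contain the daily-use analysis.** A reader might infer that 8.6.1 replaces the protocol's endpoint. The documents do not establish that. The contents list names 8.4.6, Analysis of Exploratory Efficacy Endpoints, but its text is not shown, and the Section 4 list is visible only in part. SAP 7.6.2 also mentions rescue use under a secondary and exploratory efficacy heading. What can be said is that the Section 2 table and the visible part of Section 4 omit the endpoint.

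**Avoidance of rescue is not hidden.** A reader might infer that a real fall in rescue need would go unseen. It would not, because 8.6.1 also reports the percentage of users by arm and interval. That percentage is not adjusted for follow-up either, since an early leaver has less time to become a user, but it shows avoidance directly.

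**Avoidance does not distort total dose.** The exclusion of non-users attaches only to days to first use. Total dose is summarised for each participant, so nothing in the text removes non-users from it.

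**Distortion of totals is conditional.** It needs dropout or diary loss to differ by arm, and no rates are given. SAP 8.2 reports disposition and early termination, so a reader could see such a difference. A per-protocol repeat, if PP Dosing means the population in SAP 6.4, requires a Day 180 Visit and so roughly equalises follow-up, but only by restricting to completers. Caplet counts at visits (Protocol 6.5.1) might recover some doses missing from the diary; 8.6.1 does not say whether they are used. None of this supplies a follow-up-adjusted ITT comparison.

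The decision not to impute rescue use is not itself a fault, and the remedy below needs no imputation.

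**Conclusion.** The point holds in a limited form. SAP 8.6.1 plans a total that depends on length of observation and a time to first use that leaves out non-users, while the protocol names mean daily use and the visible SAP endpoint lists omit it.

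For total dose, the bias runs toward apparently lower rescue use in the arm with more loss. It is about 5% at 20% against 10% dropout, about 8% at 20% against 5%, and zero when loss is equal. These figures rest on assumed rates, uniform exits and simple summing of observed doses.

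For days to first use, the users-only mean understates a difference in avoidance under the models tried, and the adjacent percentage of users largely makes up for that.

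The endpoint is exploratory, the summaries are descriptive, and both lie outside the testing hierarchy in SAP 7.4. This is a minor improvement.

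**What to change.** 1. Add the protocol's daily-use endpoint to the exploratory lists in SAP Sections 2 and 4, and confirm or add its analysis in 8.4.6. State what the change is measured from, because study acetaminophen is first dispensed on Day 0.
2. In 8.6.1, summarise mean daily dose by arm for each interval, defined as total dose divided by observed diary days in that interval, with non-users counted as zero. The raw total can stay as a supporting line.
3. Report time to first use by Kaplan-Meier for all ITT participants, censored at the last diary day, beside the existing percentage of users. Time to first use is not a protocol endpoint, so this governs how the statistic is presented if it is kept.
4. In the same edit, define PP Dosing or replace it with a population from SAP Section 6, which does not define that label.

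The cost is a few lines of SAP wording and two programs. The daily eDiary records are already planned, so no new data collection is needed and no clinical rule changes.

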8.7. Interim Assessment

The interim assessment will be conducted by the IDMC; the details of the procedure are described in the IDMC Charter. Given that much of the programming to derive the estimates will come from this SAP, a summary of the process is outlined below.

After 76 subjects either discontinue or complete the study, representing 50% of the original sample size, the interim analysis will be performed. The interim analysis will be used to re-estimate the sample size based on the following decision rule; the trial may be halted for futility based on the interim analysis results.

- If the conditional power is in the unfavorable zone, <39.6%, the study will be halted; no additional participants will be enrolled.
- If the conditional power is in the promising zone, 39.6% to 80%, the sample size will be increased to a final sample size (N₂, ≤250), where N₂ satisfies the condition that the conditional power is 80%.
- If the conditional power is in the favorable zone, >80%, the study will continue with the original sample size of 152.

The interim assessment will follow the method described in the published paper by Mehta and Pocock,² which states that if "the sample size is only increased when the interim conditional power falls within a certain 'promising zone' then the conventional test will indeed protect the type-I error." The minimum of conditional power is not so small as to result in an inflated overall type-I error using a conventional final analysis. Therefore, implementing the interim analysis for the reestimation of sample size should protect inflation of the type I error rate.

8.7.1. Monitoring of the Primary Efficacy Endpoint

The monitoring question that will be addressed by the IDMC during the clinical investigation is as follows:

• Does the conditional power from the interim evaluation of the primary efficacy endpoint equal or exceed 39.6%, allowing a re-estimation of the target sample size?

8.7.2. Site Surveillance

Not all of the data supplied to the IDMC will be fully monitored at the time of the interim assessment. Given that the data extract for the IDMC will occur during the course of the study, it may not be feasible to have all of the necessary study subjects' data monitored, and the database will not be locked. The IDMC will be charged with identification of any investigational sites where the interim data are either incomplete or inconsistent and should not be used in the interim calculation of response. Incomplete or inconsistent data may indicate that the study subject selection by the investigational site requires further review. Possible action, as a result of the recommendation from the IDMC, will include suspension of enrollment for an individual site until the study subject case records can be fully monitored. The objective of the intra-site surveillance is to ensure that failure to complete the study is not a result of inappropriate study subject selection, or failure to adhere to the requirements outlined in the protocol.

Independent of the decisions made by the IDMC, the final analysis will be performed using all of the final and monitored data.

The research questions that will be addressed by the IDMC, relative to site surveillance, covers

efficacy:

[figure not shown]
- Based on the pattern of missing or incomplete data, coupled with the attrition rate, does the IDMC recommend continuing enrollment of study subjects at each of the active investigational sites?
- Are there significant differences within each of the treatment arms across the active sites that may affect the poolability of the results across sites?

The IDMC will make one of following non-binding recommendations to the sponsor after conducting the interim assessment:

- Continue enrolling subjects to the pre-specified target sample size
- Continue enrolling subjects to a sample size that exceeds the pre-specified target sample size but less than or equal to the maximum sample size of 250
- Stop enrolling subjects based on futility

An alpha level adjustment will not be necessary for the conditional power procedure if the conditional power for the primary endpoint is $\geq 39.6\%$.

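### Does the IDMC's freedom to leave sites out of the interim calculation, with no stated information fraction or order of review, call for a change to the SAP?

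*SAP*

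**What the plan says.** SAP 8.7 sets the timing: "After 76 subjects either discontinue or complete the study, representing 50% of the original sample size, the interim analysis will be performed". Conditional power below 39.6% means halt, 39.6% to 80% means increase up to 250, and above 80% means stay at 152. SAP 8.7.1 frames the monitoring question the same way: "Does the conditional power from the interim evaluation of the primary efficacy endpoint equal or exceed 39.6" percent. For the mechanics, SAP 8.7 says that "the details of the procedure are described in the IDMC Charter", and adds: "Given that much of the programming to derive the estimates will come from this SAP, a summary of the process is outlined below".

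SAP 8.7.2 explains why some sites may be set aside. The interim extract will be only partly monitored and "the database will not be locked". The IDMC is therefore to identify "investigational sites where the interim data are either incomplete or inconsistent and should not be used in the interim calculation of response". The section also has the IDMC consider differences between sites within each arm. It limits the reach of the exclusion: whatever the IDMC decides, "the final analysis will be performed using all of the final and monitored data". It also describes the outcome as advice: "The IDMC will make one of following non-binding recommendations to the sponsor after conducting the interim assessment".

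Reading the calculation of response as the input to conditional power is an inference. It is a natural one, since conditional power is the only interim calculation described.

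**The concern.** Two things are left open. First, if a site is excluded, fewer than 76 participants contribute. The same data can then give a conditional power on either side of 39.6%, depending on whether the analyst uses the retained number over 152 or keeps 76/152. Second, the grounds for exclusion carry no threshold, and nothing says that sites are chosen before the comparison is opened. The Protocol synopsis (Number of Participants) describes the interim as unblinded and comparative, and the by-arm review of sites sits in the same section as the exclusion. A committee that has seen the results could, in principle, move the trial out of the halt zone by its choice of sites. At stake is the recommendation to stop or enlarge a Phase 3 trial, and possibly the type I error, because the final test uses an unadjusted critical value.

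**Working it through.** **Inputs.** From SAP 5: difference 1, SD 2.18, 1:1 allocation, two-sided 5%, N = 152, maximum 250. From SAP 8.7: interim at 76, zone limits 39.6% and 80%. Assumed, because the supplied text does not give them: ten equal sites with one excluded (8 to 25 sites as the range), and conditional power computed under the current trend.

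**The plan's own figures.** The noncentral t test gives power 0.802 at N = 152 and 0.951 at N = 250, as in SAP Table 4. The smallest conditional power at which an unadjusted 1.96 remains valid, with a maximum of 250, is 39.0% at 76/152. The stated 39.6% is therefore slightly conservative. With 68 retained the figure is 39.3%, and with 60 it is 39.7%. So 39.6% stays sufficient down to about 62 retained participants.

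**Same data, two fractions.** With n participants used and observed difference d, z = d√n / (2 × 2.18). With m the number that the calculation assumes,

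CP = 1 − Φ[ (1.96√152 − z√m)/√(152 − m) − z√(152 − m)/√m ].

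Take n = 68 and d = 0.64, so z = 0.64 × 8.246/4.36 = 1.210.

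- m = 68: (24.164 − 9.982)/9.165 − 1.345 = 0.202, so CP = 42.0% (increase).
- m = 76: (24.164 − 10.552)/8.718 − 1.210 = 0.351, so CP = 36.3% (halt).

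The second line is inconsistent: its z has the precision of 68 people but is weighted as if it came from 76.

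**How often it matters.** With a tenth of 76 removed, n = 68.4 and the standard error of the difference is 4.36/√68.4 = 0.527. The halt line is an observed difference of 0.624 when the fraction is recalculated and 0.661 at 76/152, a window of 0.037. At a true difference of 1.0:

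- P(halt), recalculated = Φ((0.624 − 1)/0.527) = 23.8%
- P(halt), 76/152 = Φ((0.661 − 1)/0.527) = 26.0%

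The halt-or-increase decision therefore differs in about 2.2% of trials (0.9% for 25 sites, 2.8% for 8). A further 2.9% differ at the 80% edge, making 5.1% in all. At that edge the consequence is a final N of roughly 154 to 170 instead of 152.

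**Power and error by simulation** (exclusion unrelated to outcome; power at a true difference of 1.0, error under no effect):

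| | All 76 used | One site out, recalculated | One site out, 76/152 kept |
|---|---|---|---|
| Power, halt followed | 72.7% | 71.4% | 69.7% |
| Power, halt not followed | 83.4% | 83.4% | 83.2% |
| One-sided error, halt not followed | 0.0244 | 0.0245 | 0.0243 |

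Recalculated exclusion costs 72.7 − 71.4 = 1.3 points. The miscalculation costs a further 71.4 − 69.7 = 1.7 points.

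**Worst-case bound on selection.** Suppose the least favourable site were always dropped under no effect, which no rule in the SAP provides for. One-sided error is then 0.0256 to 0.0261 with the halt not followed and 0.0221 to 0.0235 with it followed, for 8 to 25 sites. With the two least favourable of ten dropped, it is about 0.0255 even with the halt followed.

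**The case for a change.** The best counter-argument is that the SAP says it will drive much of the interim programming, so a programmer working from it alone must choose the fraction unaided. A sentence would cost little now and could not credibly be added after unblinded results are seen. Non-binding status does not remove the point, since the sponsor still receives a different recommendation from the same data. On selection, dropping the two least favourable of ten sites whenever full-data conditional power falls below 39.6% would cut the chance of a futility stop under no effect from 89.5% to 59.1%.

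Part of this stands. The supplied text is silent on both points, and the selection example shows why choosing sites before the comparison is opened is good practice. But that example describes a committee selecting on outcome, while SAP 8.7.2 gives a data-quality ground and assigns the task to an independent committee. Thresholds and order of review are the kind of detail SAP 8.7 sends to the Charter. On the fraction, the 50% in SAP 8.7 describes when the interim is triggered. It does not tell anyone to hard-code 0.50 after participants are removed, and an analyst computing conditional power will ordinarily use the number in the statistic.

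**Conclusion.** No change to the plan follows. The gap is real but is one of detail that a competent analyst fills correctly, in a section that names another document for its procedure. The provision itself is a reasonable safeguard when interim data are partly unmonitored and unlocked.

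On the sensible reading, leaving out one of ten sites for reasons unrelated to outcome costs about 1.3 points of power if the halt is followed and does not take one-sided error above 0.025. The 39.6% limit still holds at that level of exclusion. An analyst who wrongly kept 76/152 would change the halt-or-increase decision in about 2.2% of trials in which such an exclusion occurs. Adverse selection in its worst form lifts one-sided error to about 0.026; with two or more sites dropped it can exceed 0.025 even when the halt is followed. The final estimate is unaffected by selective omission because all sites return to the final analysis.

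These figures rest on SD 2.18, equal sites, an assumed site count and current-trend conditional power. If conditional power used the planned difference, the pooled disagreement rate would be 5.6% in place of 5.1%. The Charter, the text of SAP 8.4 and one figure in SAP 8.7.2 were not available.
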